cardiopulmonary exercise testing. If the preliminary results of this randomized phase Il study demonstrate that oxygen or high flow rate affect dyspnea intensity, the next step will be to conduct a larger multi-institutional, randomized controlled trial that is adequately powered to compare HFOx with a control intervention, particularly in the home setting. This would be a logical extension of the proposed study because the use of HFOx has predominantly been limited to the hospital setting. The technology that allows this device to be used at home in an affordable manner is just now becoming available (i.e., Flowrest device). Once the efficacy of HFOx is confirmed, patients will have *much more* access to this therapeutic measure. The proposed study has the

Figure 3. Study Flow Chart.

potential to greatly improve patients' symptom burden, function, and quality of life.

C. RESEARCH DESIGN AND METHODS

C.1. Overall study design (Figure 3). This is a 2x2-factorial, double-blind, randomized, controlled trial of HFOx, HFAir, LFOx, and LFAir in non-hypoxemic cancer patients with dyspnea. We plan to enroll 50 patients in total. Enrolled patients will first complete a baseline structured exercise session with LFAir and return 3±2 days later to be randomly assigned to receive one of the four study interventions during the second structured exercise session. We will use a computer-generated sequence in permuted blocks for randomization, stratified by baseline dyspnea modified Borg Scale and work rate. Even with 2 different flow rates, patients and research staff will be blinded to the gas (i.e., oxygen v. air); thus, this will remain a double-blind study. On the basis of our experience conducting symptom control trials, we believe this study design is feasible and will not be an undue burden for patients. The rationale for the current study design is as follows:

- **Factorial design**—This will allow us to examine the oxygen and high flow effects separately while providing preliminary data about synergism between oxygen and flow.
- **Parallel design**—This design will minimize study burden and attrition compared with a crossover study that requires 5 exercise sessions. We will adjust for inter- individual differences by accounting for both baseline dyspnea score and maximal work rate.

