- **Baseline exercise sessions on day 1**—Patients will first complete an incremental exercise test to familiarize themselves with the cycle ergometer and to identify their maximal work rate. They will then complete a structured exercise session with cycle ergometry at a constant work rate of 80% peak with LFAir, which will inform us of their dyspnea response and isotime.
- Use of LFAir at baseline test—Neither LFAir nor LFOx has been found to improve dyspnea in non-hypoxemic patients. This will address the placebo effect with nasal cannula use.
- Inclusion of HFOx and HFAir arms—To our knowledge, HFOx has not been tested in non-hypoxemic cancer patients. No study has examined the therapeutic role of HFAir in any patient population.
- **Inclusion of LFOx arm**—Although LFOx was found to be ineffective compared with LFAir during the 6-minute walk test, its utility has not been tested with cycle ergometry in cancer patients.
- Stratification—To minimize the possibility that baseline dyspnea and exercise performance will affect the outcome, we will stratify patients by this baseline dyspnea modified Borg Scale score at rest (0-3/10 vs. 4-7/10; >7/10 will be excluded) and by their work rate during the first structured exercise session (≤50 W vs. >50 W). The objective of stratified randomization is to ensure a balance of the treatment groups with respect to the various combinations of predictive variables (i.e., the baseline Borg scale and work rate). This will ensure that a similar number of patients from each strata are randomly assigned to each treatment arm but will not require a similar number of patients in each strata. Thus, stratification should not affect the enrollment rate.

2014-0971 Rev. 9/17/18 Page 6 of 15

C.2. Eligibility criteria. The eligibility criteria are shown in Table 1. The rationale for including patients with obstructive and restrictive lung disease in this study is that the mechanisms of dyspnea relief (e.g., trigeminal nerve stimulation and decreased breathing effort; see Figure 1) are applicable to both types of pulmonary disorder. To ensure homogeneity in the study population and patient safety, we will exclude patients with severe obstructive airway disease (FEV1/FVC <70% post bronchodilator and forced expiratory volume in 1 second <30% predicted).

Table 1. Study Eligibility Criteria

Inclusion Criteria

- 1. Diagnosis of cancer, with evidence of primary or secondary lung involvement

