⁶ Validated 12-item questionnaire to assess the quality of dyspnea in cancer patients during the previous few days (Tanaka *et al.* 2000). Each item has a score between 1 and 5, for a maximum of 60.

⁷ The Baseline dyspnea index (BDI) is a validated scale used to assess dyspnea under 3 domains: 1) functional impairment, which examines the impact that dyspnea has on the ability to carry out daily activities; 2) magnitude of task, which examines the type of task that results in dyspnea; and 3) magnitude of effort, which establishes the level of effort that leads to dyspnea. BDI ranges from 0 (very severe impairment) to 4 (noimpairment) for each domain, with a total score of 0 to 12.(Mahler *et al.* 1984, Mahler and Wells 1988, Witek and Mahler2003)

⁸ The Modified Dyspnea Borg Scale-Intensity is the primary outcome measure, a 0 (no dyspnea) to 10 (worst dyspnea) ratio scale validated for rating dyspnea severity (Dorman *et al.* 2007,

Powers and Bennett 1999); this will be measured every minute during exercise testing. Modified Dyspnea Borg Scale-Unpleasantness is one of the secondary outcomes.

⁹ Heart rate, respiratory rate and blood pressure will be measured at baseline and every 2 minutes during the exercise sessions. Continuous oxygen saturation and electrocardiogram monitoring will be provided during the exercise sessions, and documented every 2 minutes during testing. During the cool down period, these will be measured every 1 minute

¹⁰ Work rate (Watts) is calculated as follows: resistance of the flywheel x distance/revolution (m/revolution) x pedaling rate (revolution/min) x time (minute). One Watt is equivalent to 6 kg·m·min⁻¹. It will be measured continuously during exercise testing. We will also document symptoms (e.g. fatigue and leg discomfort) q2min during exercise testing, as well as reasons for stopping (e.g., breathlessness, fatigue, and leg discomfort) and the duration of exercise.

¹¹ Device settings include FiO₂, oxygen flow, and temperature.

¹² Adverse effects related to supplemental oxygen use, such as dry eyes, dry nose, nasal moisture, and anxiety, will be assessed using a numeric rating scale from 0 (not at all) to 10 (worst possible) before and after the intervention.

¹³ We will assess blinding (oxygen v. air) and global impression (better/no change/worse) of patients and research staff.

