C.9. Exertional dyspnea clinical trials (Hui et al. 2014). Our department has an invested interest in developing novel therapeutics for exertional dyspnea in cancer patients. We have just completed a double-blind, randomized controlled trial to determine the effect of subcutaneous fentanyl on exertional dyspnea. After a baseline 6- minute walk test, patients were given fentanyl or a placebo and then asked to repeat the test. We enrolled 20 non-hypoxemic cancer patients in 5 months, with 100% completion. We also currently have 2 active double-blind, randomized controlled trials with fentanyl pectin nasal spray (expected to complete accrual by Feb 2015) and fentanyl buccal tablet. Because these opioid trials can only enroll patients who are opioid tolerant there should be many eligible patients for the proposed study.

C.10. Co-interventions. We will ask patients to use their usual inhaled medications on the day of the test as appropriate.

C.11. Training of research staff. An orientation will be held with all research staff involved in this study to introduce them to the study design and standardize the provision of each intervention. Particular attention will be paid to ensuring that research staff provide patients with proper instructions so they understand the study assessments. We will also have several mock-ups for practicing the study procedures.

C.12. Data Safety Monitoring Board (DSMB). The MD Anderson DSMB will be providing monitoring for patient safety and data quality assurance purposes.

D. STATISTICAL ANALYSIS

D.1. Sample size justification. Using 10 patients per arm (assuming 20% attrition, 50 total), we will have 86% power to detect a 1-standard deviation (SD) main effect and 86% power to detect a 2-SD interaction effect (assessed as the difference between the joint effect and an additive effect) with an alpha of 5%. These are large effects, but the main objective is to obtain preliminary estimates of effect sizes. We have expressed the treatment effects as multiples of the standard deviation because we do not have valid preliminary estimates of the within-group standard deviations on which to base these calculations.

D.2. Analysis plan. For the primary analysis, we will use a general linear model, with a Borg dyspnea score at isotime as the outcome variable and including the following

2014-0971 Rev. 4/20/2017 Page 12 of 15

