To estimate the effects of oxygen and flow rate on physiologic function (respiratory rate and oxygen saturation) and exercise capacity (work rate and exercise duration), we will use mixed-effects linear models because most of these are measured repeatedly over time. Given the limited number of patients, the results will be considered exploratory. Adverse events will be assessed using a numeric rating scale from 0 to 10 before and after intervention. Differences in these scores for each type of adverse event will be analyzed using general linear models, as described above for the primary endpoint.

2014-0971 Rev. 4/20/2017 Page 13 of 15

E. DATA CONFIDENTIALITY PROCEDURES

Health information will be protected and we will maintain the confidentiality of the data obtained from the patient's chart.

Collection of identifiers: We will collect and securely store patients' identifiers (including name and medical record number). Each patient will be assigned a study number that will be the only identifier to figure in the analytical file and personal data will not be disclosed in any form. The key linking these numbers will be retained in a securely locked file by the investigator.

Data Storage: Protection of electronic and paper records will be guaranteed. All electronic records will be stored on password-protected institution computers behind the institution firewall. Any paper records will be classified and stored in locked files inside a locked office.

Training of personnel: Only MDACC personnel trained in maintaining confidentiality, the principal investigators and co-investigators, will have access to study records.

Data sharing: Study data will not be shared with any individuals or entities without an IRB-approved protocol. The data will be kept by the principal investigator in a locked file cabinet and password protected computers.

Final disposition of study records: PHI may be maintained indefinitely, aggregated in the future, and used for future IRB-approved research studies.

F. REFERENCES

1. Ats/ers statement on respiratory muscle testing. *Am J Respir Crit Care Med* 2002;166:518-624.

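### D.2 names no baseline respiratory-rate or saturation term for the physiologic models, although both are recorded in the pre-randomisation LFAir test; using them would tighten these exploratory estimates at almost no cost

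*Combined protocol and SAP*

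**What the plan says.** **Analysis (D.2).** For respiratory rate, saturation and exercise capacity the plan will "use mixed-effects linear models because most of these are measured repeatedly over time". It gives no covariate list for these models and calls the results exploratory because of the small sample. The one explicit covariate set in D.2 belongs to the Borg model: flow, oxygen, their interaction, work rate and resting dyspnea. It is carried over to the longitudinal Borg model. The generic equation in D.2 also allows for unspecified further terms.

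**Adjustment (C.1, parallel-design rationale).** Differences between patients are to be handled by "accounting for both baseline dyspnea score and maximal work rate".

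**Data collected.** On day 1, before randomisation, patients do an incremental test. "They will then complete a structured exercise session with cycle ergometry at a constant work rate of 80% peak with LFAir" (C.1). Table 2 schedules vital signs before and during both structured tests. Footnote 9 says: "Heart rate, respiratory rate and blood pressure will be measured at baseline and every 2 minutes during the exercise sessions". The same footnote has saturation monitored continuously and documented every 2 minutes. C.7 has the structured exercise and its assessments repeated 3±2 days later on the assigned intervention.

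**The concern.** Each patient supplies control-condition readings of respiratory rate and saturation, on the same ergometer protocol, a few days before receiving the randomised gas and flow. They precede randomisation, so they are valid covariates, and they are the most direct predictors of the second-session values that the trial collects. Resting dyspnea and work rate are only indirect stand-ins for them.

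Patients are likely to differ a good deal in exercise respiratory rate, since both obstructive and restrictive lung disease are eligible. In a parallel design with about 10 patients per arm, those differences stay in the error of the oxygen and flow contrasts, and chance imbalances pass into the estimates. B.5 relies on changes in physiologic measures to explain how relief of dyspnea works, and the trial's stated product is preliminary effect sizes. Precision is therefore what is at stake.

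**Working it through.** **1. The plan's own figure.** D.1 states: "Using 10 patients per arm (assuming 20% attrition, 50 total), we will have 86% power to detect a 1-standard deviation (SD) main effect". It claims the same power for an interaction of 2 SD. A main effect compares 20 with 20.
- SE = SD × √(1/20 + 1/20) = 0.316 SD. Noncentrality = 1/0.316 = 3.162.
- Interaction: SE = SD × √(4/10) = 0.632 SD. Noncentrality = 2/0.632 = 3.162, so the power is the same.
- Noncentral t, two-sided 5%: 86.9% (38 df), 86.8% (36 df), 86.7% (34 df, with two covariates).

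The 86% reproduces, and 40/(1 − 0.2) = 50 gives the total. The sample-size statement is sound. It is not made for respiratory rate or saturation, and is used here only as a scale.

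**2. Why the mixed model alone does not help.** Write a second-session reading as treatment + patient effect + session effect + reading error. Treatment varies only between patients. With K readings each, the variance of a main-effect contrast is (1/20 + 1/20) × (patient variance + session variance + error variance/K). A random intercept estimates that sum but does not shrink it. Conditioning on the patient's baseline mean multiplies it by (1 − r²), where r is the partial correlation of the two session means given the other terms.

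**3. Gain, one value per patient, 40 completers.** The inputs are SE 0.316 SD, 34 df without the term and 33 with it, and t multipliers 2.032 and 2.035. With the term, SE = 0.316 × √[(1 − r²)(1 + 1/32)], where the last factor charges for estimating one more coefficient. D.1 says of the SDs that "we do not have valid preliminary estimates of the within-group standard deviations", so everything stays in SD units. **r is an assumption.**

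| r | SE (SD) | 95% half-width (SD) | Power at 1 SD | Equivalent patients |
|---|---|---|---|---|
| term absent | 0.316 | 0.643 | 86.7% | 40 |
| 0.1 | 0.320 | 0.650 | 85.9% | 39 |
| 0.2 | 0.315 | 0.640 | 87.0% | 40 |
| 0.3 | 0.306 | 0.623 | 88.6% | 43 |
| 0.5 | 0.278 | 0.566 | 93.7% | 52 |
| 0.7 | 0.229 | 0.467 | 98.8% | 76 |

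Equivalent patients = 40/[(1 − r²)(1 + 1/32)]; at 0.5 this is 40/(0.75 × 1.031) = 51.7. The half-widths break even at r ≈ 0.18. If 50 patients complete, as C.7 says, the half-width at r = 0.5 falls from 0.570 to 0.500 SD.

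**4. Plausible r (assumed variance splits).** With patient, session and reading variances of 0.5, 0.2 and 0.3 and three readings, r = 0.5/(0.5 + 0.2 + 0.1) = 0.62 and the SE ratio is 0.79. Across four such splits with 3 or 5 readings, r runs from 0.27 to 0.79, and the SE falls by 2% to 38%.

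**5. Form of the covariate.** The table assumes one baseline value per patient. A baseline reading matched minute by minute is a different analysis: its single slope mixes within- and between-patient association and is attenuated. In simulation (40 patients, 4 readings per session, random intercept, assumed variance splits, independent reading errors), the main-effect SE fell as follows:
- session-mean r about 0.60: about 9% with the matched reading, about 20% with the session mean;
- session-mean r about 0.70: 13–14% with the matched reading, 27–28% with the session mean.

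**6. Saturation.** If r is 0.7 on air and 0 on oxygen (a ceiling; assumed), a common slope cuts the SE by only about 5–6%.

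**The case against.** **The plan is silent; it does not exclude the term.** A reader might infer that D.2 rules out baseline values or throws them away. The text does not support that. It names a model class, lists no covariates, does not say whether first-session readings enter the repeated-measures model, and leaves room for further terms. This stands, and limits the point to what the plan fails to name. Open-ended wording does not fill the gap, because it would leave covariates to be chosen with about 40 patients' data in hand.

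**A broken design promise.** It is also tempting to say that the parallel design was justified by outcome-specific baseline adjustment. C.1 justifies it by lower burden and attrition, and then names two adjusters. It promises nothing more for secondary outcomes.

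**Saturation has little to gain.** Entry requires saturation above 90%, exercise ends below 88%, and patients with significant hypoxemia count as dropouts. The baseline range is narrow, and values on oxygen may sit near a ceiling. This stands; the case is mainly about respiratory rate.

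**The stakes are low.** The outcomes are secondary and exploratory, and the stated trigger for a larger trial (B.5) is dyspnea intensity. At r = 0.3 the half-width moves only from 0.64 to 0.62 SD. This stands too, and sets the severity.

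**Conclusion.** The point holds as a cheap gain in precision, to be **considered**. D.2 names no baseline respiratory-rate or saturation term, the data for one are already scheduled, and a random patient effect on second-session data does not replace it. With 40 completers and one baseline value per patient, the 95% half-width for a main effect goes from 0.64 SD to 0.62, 0.57 or 0.47 SD at partial correlations of 0.3, 0.5 or 0.7, with nothing gained below about 0.2. The documents give no correlation, so the true gain is unknown. It is probably worthwhile for respiratory rate and small for saturation.

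Two stronger readings should be resisted. One is that the estimates would be biased: allocation is randomised, so leaving the term out costs precision only. The other is that the point undermines the sample size or the primary Borg analysis: D.1 reproduces, and the finding concerns these two physiologic outcomes alone.

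**What to change.** In D.2, state that the second-session respiratory-rate and saturation models include, as one fixed covariate per patient, the mean of the same measure over the baseline LFAir constant-load test, centred at the mean of all patients. List it beside flow, oxygen, their interaction, work rate and resting Borg. Modelling both sessions jointly is an acceptable alternative. The session mean recovers more precision than a minute-matched reading and is available however long the second session lasts.

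If the saturation slope is allowed to differ between oxygen and air, the centring is essential. D.2 reads the oxygen effect from b2 and b2 + b3. With an uncentred covariate those would be effects at a saturation of 0%; with a centred one they remain the effects at the average baseline.

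**Cost.** One sentence; no new data, visits or staff. The term uses one model degree of freedom, or two for saturation with separate slopes. With one term, if the correlation is near 0.1, the loss is under 1 power point (86.7% to 85.9% on D.1's 1-SD scale).

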During the second session, 3±2 days later, patients will be asked to repeat the structured exercise with one of the four study interventions. The study assessments conducted on the first day will be repeated. We will use the constant work rate test for the comparison because it has been found to be more responsive for dyspnea than have incremental tests (Teunissen et al. 2007). A gas exchange analysis will not be conducted because the high flow and oxygen content can interfere with measurements of VO2 (ml/kg/min), VO2 (L), VCO2 (L), VE (L), PetO2 (mm Hg), and PetCO2 (mm Hg), making accurate assessments infeasible. After consulting with our pulmonary collaborator and exercise physiology team (PROSPR), we have decided to measure the work rate and use this as a factor for stratification.

Although we do not expect patients to experience desaturation during exercise based on our previous studies, if we find significant hypoxemia during testing with LFAir or HFAir (and even LFOx and HFOx) arms, patients will not be able to continue with this study and will be considered as dropouts. The termination point is defined by (1)

2014-0971 Rev. 9/17/18 Page 9 of 15

participant volitional fatigue, (2) abnormal hemodynamic responses to increasing workload, (3) inability to maintain bike cadence, (4) arrhythmias detected on the ECG including changes suggesting ischemia, (5) loss of any monitoring signals, or (6) hypoxemia [O2 saturation <88%] while exercising. Patients will be monitored throughout structured exercise testing, and will have access to urgent medical care if needed. Because this study is designed to induce dyspnea with exercise and some participants had to stop the exercise testing due to leg cramps before they became dyspneic, we will ask study participants not to continue with the rest of the study if their maximum level of dyspnea Borg scale intensity is less than 4/10 by the end of the first incremental test (in keeping with inclusion criteria #2). We will enroll a total of 50 patients who completed all 3 exercise tests and had dyspnea of at least 4/10 at the end of the first incremental test.

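### Tests stopped for hemodynamic, cardiac or hypoxemic events do not enter the adverse-event comparison between arms, which is confined to 0-10 ratings of oxygen-related effects

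*Combined protocol and SAP*

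**What the plan says.** The last paragraph of D.2 states how adverse events are measured, "Adverse events will be assessed using a numeric rating scale from 0 to 10 before and after intervention", and how they are compared: "Differences in these scores for each type of adverse event will be analyzed using general linear models, as described above for the primary endpoint". The documents give no other definition or analysis of adverse events.

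Table 2, footnote 12 gives the content of the rating: "Adverse effects related to supplemental oxygen use, such as dry eyes, dry nose, nasal moisture, and anxiety".

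C.7 lists six termination points for an exercise test. Three are clinical events observed by staff or monitors: points (2) and (4), "2) abnormal hemodynamic responses to increasing workload, (3) inability to maintain bike cadence, (4) arrhythmias detected on the ECG including changes suggesting ischemia", and point (6), "hypoxemia [O2 saturation <88%] while exercising". C.7 also classes patients with significant hypoxemia during testing as dropouts, and it counts toward the 50 only patients who complete all three exercise tests.

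Footnote 10 records "reasons for stopping (e.g., breathlessness, fatigue, and leg discomfort", with those symptoms as examples. C.3 says that reasons for dropout will be documented. D.2 analyses neither.

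**The concern.** The hazards for which the protocol itself stops a test are not the things that its adverse-event analysis measures. An arrhythmia, an ischemic ECG change or a desaturation either happens or does not, and is seen on a monitor. It has no item on a patient-rated scale for effects such as a dry nose. A model of before-after rating differences therefore has no place for it.

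What is at stake is the safety statement in the report. If D.2 is followed exactly, that statement rests on the rating differences. Several tests in one arm could have been stopped for cardiac or hypoxemic reasons and the statement would be unaffected. The trial is meant to lead to a larger randomized study (B.5), whose planners would want the count by arm.

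**Working it through.** **1. The three clinical stopping events against each provision that might capture them**

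| Provision | What it gives | By-arm count of these stops? |
|---|---|---|
| D.2 adverse events, footnote 12 | Before-after difference in 0-10 ratings of oxygen-related effects | No: the event is not a rating |
| Footnote 10, reasons for stopping | Recorded for each test | No analysis stated |
| C.3, reasons for dropout | Documented | No analysis stated |
| D.2, completion | One proportion with a 95% interval | No: neither arm nor cause |
| D.2, saturation and exercise duration | Mixed models for oxygen and flow effects, exploratory | No: a stop ends the saturation series and shortens the duration, whatever its cause |
| C.12, DSMB | Monitors patient safety | Contents of its reports not stated |

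The data are collected, but no row yields the count.

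**2. Who could be missing from the ratings**

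Under C.7 a patient with significant hypoxemia becomes a dropout, and only completers of all three tests count toward the 50. A patient stopped in the randomized session may therefore have no rating after the intervention. The D.2 provision for multiple imputation (more than 10% of patients with missing data) could fill in such a rating, but it would not create an event count.

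**3. Denominators, from D.1**

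- 10 per arm × 4 arms = 40. With 20% attrition, 40/(1 − 0.20) = 50, as stated.
- Each factor level has 2 × 10 = 20 patients.
- The stated power also reproduces. For the main effect, the noncentrality is 1/√(1/20 + 1/20) = 3.162. For the interaction, it is 2/√(4/10) = 3.162. Two-sided 5% with 36 df gives 86.8%, against the stated 86%. Nothing below depends on this figure.

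**4. What a count would say at this size**

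The documents give no event rates, so these figures are illustrations.

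- Zero events, two-sided exact 95% upper limit = 1 − 0.025^(1/n). For n = 10: 30.8%. For n = 20: 16.8%. If 50 patients start the randomized session, a factor level has 25 and the limit is 13.7%.
- One event in 10: 10% (exact 95% interval 0.3% to 44.5%). Two in 10: 20% (2.5% to 55.6%).
- Chance of at least one event among 20 patients = 1 − (1 − p)^20. For assumed p of 2%, 5% and 10%: 33%, 64% and 88%.
- Power of Fisher's exact test for an assumed 5% against 20%, with 20 per side: 17%.

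The last line shows that the count should be descriptive and not a test.

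**The case against.** The strongest reply is that little is actually lost. Stopping reasons go on the form (footnote 10), dropout reasons are documented (C.3), saturation is monitored continuously and modelled by factor, and a DSMB watches patient safety (C.12). Safety is not among the three stated objectives, and at this size no comparison of stops could be more than descriptive. Stops during supervised cycling would also say little about safety at home, the setting that B.5 has in mind for the next trial.

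Most of this stands, and it limits the point in four ways.

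- A reader might infer that these events go unrecorded or unmonitored. The documents say the opposite. The examples in footnotes 10 and 12 are also open lists, so an arrhythmia could be written down as a stopping reason.
- A reader might infer that hypoxemia is absent from the comparison of arms. It is not, because saturation is modelled for oxygen and flow. That model is exploratory, however, and does not count patients stopped below 88%.
- A reader might suppose that a patient stopped for arrhythmia scores zero on every rated item. Nothing supports this. Such a patient may rate anxiety highly or have no later rating at all.
- A reader might infer from the columns of Table 2 that no slot exists for the later rating. The table header is broken in the text available, and D.2 and footnote 12 both state before-and-after timing.

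None of this supplies the missing count. D.2 states what adverse events are and how they are compared, and the stops are outside that statement.

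**Conclusion.** The point holds as a gap in the definition, analysis and reporting of adverse events by arm. It is not a gap in bedside monitoring or data capture. The plan as written permits a report of no adverse-event difference while the arms differ in hemodynamic, cardiac or hypoxemic stops, and D.2 contains nothing that would reveal this.

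The size cannot be forecast, because the documents give no event rates. In a ten-patient arm each stop is 10 percentage points, and even an arm with none would be compatible with a true rate of up to 30.8%. The conclusion rests on reading D.2 and footnote 12 together as the whole adverse-event analysis. The documents do not show what the DSMB receives, so they do not establish that stops would go unreported to it.

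The change should be made before analysis. It does not affect the primary endpoint or the sample size.

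**What to change.** In D.2, add to the adverse-event analysis:

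1. A descriptive table of tests stopped under each of the six C.7 termination points, by session and, for the second structured (randomized) session, by arm and by factor level.
2. The denominator for that session: everyone who starts it, whether or not they complete it or give a rating afterwards.
3. Two-sided exact 95% intervals and no hypothesis test.
4. A separate listing of any arrhythmia, ischemic change or hypoxemia recorded during exercise or cool-down that did not stop a test.

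In footnote 10, code the stopping reason by the six C.7 termination points, in addition to the symptoms already given there.

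The cost is one coded field on a form that already takes the stopping reason, one table with a short listing, and a few sentences of analysis plan. The intervals will be wide and the text should say so. No stopping rule, procedure or patient number changes.
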